7.3 Definitions

Serious Adverse Event: means an event that is

- fatal
- life-threatening
- persistent or significantly disabling or incapacitating
- inpatient hospitalization or prolongation of hospitalization
- congenital anomaly or defect and/or
- a significant medical incident (considered to be a serious study related event because, based upon appropriate medical judgment, it may jeopardize the subject and may require medical or surgical intervention to prevent one of the outcomes listed in this definition.)

Important Adverse Event: means an event, although not a Serious Adverse Event, which still presents an undesirable occurrence that interferes with the subject's usual activities and may be persistent or require treatment. (For example, serious rash, cough, or fever.)

Unanticipated Adverse Event: means an event that results from a study intervention and was not expected or anticipated from prior experience. This includes expected events that occur with greater frequency or severity than predicted from prior experience.

8. CORRELATIVE/SPECIAL STUDIES

8.1 Laboratory Correlative Studies

- 8.1.1 Analysis of patient plasma for biomarker development.
 - 8.1.1.1 Collection of Specimen(s) (optional):

Patients will elect whether they want to participate in this portion of the study on the consent form.

Blood Samples

- a) Blood (EDTA preserved) for research purposes will be drawn prior to radiation treatment (prefer before chemotherapy if possible) and at each follow-up along with the patient's regular labs. For each collection, up to 8 ml (1 large purple/violet tube or 2 small purple/violet tubes at 4 ml each) will be drawn.
- b) Within two hours from collection, blood will be centrifuged at 3000 RPM for 10 minutes and plasma collected. The supernatent will be aliquotted for storage at -80°C into separate tubes. The pellet will also be aliquotted and stored in separate tubes at -80°C.

Tumor Biopsy Tissue Samples

- a) Consent for obtaining tumor samples: All patients with a presumed diagnosis of pancreatic or periampullary cancer can give consent or decline consent to obtain additional tumor tissue for research purposes. In this situation, the research biopsy should be obtained only after a final diagnosis (preliminary if determined by the pathologist during the diagnostic biopsy) of pancreatic or periampullary adenocarcinoma has been reached by the pathologist. Once a preliminary/final diagnosis has been obtained, gold fiducials can be placed into the tumor for tumor tracking. In the event the patient already has a confirmed pathologic diagnosis of pancreatic or periampullary cancer, a repeat endoscopic ultrasound, CT, or laparoscopic procedure may be used to place gold fiducials into the tumor for tumor tracking. Following fiducial placement, additional tumor samples can be obtained for research purposes if the patient gives permission in the study consent.
- b) Tumor sample processing: Fine needle aspirations (FNA) and core biopsies (if possible) of tumor tissue will be immediately placed into small cryovial tubes that can be stored at -80°C. Sample tubes are immediately immersed into a canister of liquid nitrogen with forceps/tube holder until completely frozen. Samples are then transferred into the -80°C freezer until utilization for biomarker analysis.

8.1.1.2 Storage of Specimen(s)

All samples will be stored at Johns Hopkins Hospital in Cancer Research Building II at -80°C or in liquid nitrogen until utilized for analysis of biomarkers.

8.1.1.3 Site(s) Performing Correlative Studies All biomarker studies will be performed at Johns Hopkins Hospital by [name] or his staff or in the laboratory of a research collaborator. Specimen samples will also be processed in the laboratories of Stanford Cancer Institute, Memorial Sloan Kettering Cancer Center, and Metabolon, Inc.

We will utilize proximity ligation assay (PLA) to simultaneously interrogate a panel of 60-100 secreted proteins that we have developed for pancreatic cancer patients. PLA is an antibody based method of detection in which complementary single- stranded oligonucleotides are linked to each antibody pair. When the 2 antibodies bind in close enough proximity, the local concentration increases, allowing for PCR amplification of this signal. PLA is more sensitive than conventional ELISA and can be reliably multi-plexed for the detection of multiple protein panels (Fredrikkson et al). In a pilot study, we have shown that when using this method of detection (Chang et al), we can accurately identify patients with pancreatic cancer. In this study, we will expand the number of biomarkers and collect plasma at multiple time points during therapy. The goal is to identify a biomarker panel that is predictive of patient outcome and/or response to therapy. We hypothesize that not only is the pattern of secreted biomarkers important but the change in these biomarkers may be even more critical for prediction of clinical outcomes.

8.1.1.4 Coding of specimens for privacy protection

At the time of consent, each patient will be given a specific confidential identification number (IDN). Specimens will be stored under the patient's IDN. The information can be shared with other investigators listed on this protocol. Study data will be maintained in password protected computer files (protected online database through Johns Hopkins). Only research personnel will have access to this information.

8.2 Collection of Pre and Post Treatment CT/PET Scans, Treatment Planning Scans, and Treatment Plans

- 8.2.1 Data and Image Collection
 - 8.2.1.1 Pre-Linac based SBRT PET scan is recommended but not required. Post SBRT PET scans will be optional for all patients based on the opinion of the treating physician. Pre- and post-Linac based SBRT CT scans will be mandatory for all patients (PET/CT may supplement protocol CT). All images (CT and PET) will be stored electronically by JHU through the Oncospace network and be registered to each patient using the IDN. Radiation treatment plans will also be retrospectively reviewed and stored at JHU via Oncospace. The JHU database is set up to store ROI geometries and dose distributions along with the CT. This design facilitates the investigation of dosimetric effects on tumor response and complications utilizing DVH or other attributes of the 3D dose.

For Pinnacle, the data can be directly placed in the JHU database via scripts.

- 8.2.1.2 All treatment planning scans will be stored electronically by JHU through the Oncospace network and be registered to each patient using the IDN. Specific parameters will be prospectively collected such as treatment volume and dose to adjacent structures in oncospace
- 8.2.1.3 Dynamic Whole Body PET/CT

Up to 17 patients will be recruited to a sub-project that will assess the feasibility of acquiring a quantitative dynamic whole body PET/CT early after treatment. The aim of this sub-project is to assess the extent to which dynamic PET can be used to aid in the discrimination of tumor from radiation induced inflammation in a therapy assessment setting. This could potentially enable future PET/CT-based response assessment at an earlier time than the current protocol and clinical practice, 4-6 weeks post-treatment. This will allow therapy decision (success or failure) to be made earlier and management is personalized.

Unlike conventional PET imaging, which performs single-pass multi-bed imaging of the subject, the proposed framework performs multiple-pass multi-bed imaging of the subject. The objective of this alternative imaging framework as developed and validated by Johns Hopkins Department of Nuclear Medicine, and implemented by major vendors, is to quantify the pattern of tracer uptake within the imaging duration, moving beyond conventional static imaging. This approach enables enhanced quantification of radiotracers uptake by tumors, and has the potential to enable improved differentiation of tumor recurrence from inflammation, and is hypothesized to arrive at improved assessment of therapy response and prediction of outcome.

In this sub-set of patients who consent to undergo this research imaging, two ¹⁸F-FDG dynamic whole body PET/CT scans will be obtained using the novel protocol of dynamic whole body data acquisition. Patients participating in this sub-project will have a PET/CT study performed in a dynamic whole-body mode at baseline and on day 5 of SBRT treatment. All PET/CT studies will be acquired on the Biograph mCT at the Johns Hopkins PET Center. Dynamic whole-body PET/CT scanning will last approximately 45 minutes, while single-pass whole-body PET/CT imaging last under 30 minutes, although the total duration of the patient visit is likely to be 2-3 hours. Each PET/CT study will involve intra-venous administration of 0.15 mCi / kg of ¹⁸F-FDG (maximum 17.5 mCi), similar to clinical FDG dose. Low-dose CT will be acquired at the same imaging session, similar to clinical protocol. The total effective dose for each PET/CT study is <0.4 rem for the CT and <1.2 rem for the PET.

9. INVESTIGATOR RESOURCES

9.1 Qualifications

The study staff will include, but is not limited to, the Principal Investigator, Co-Investigators, research coordinators, research nurses, and any residents or fellows working with the physicians.

All study staff have completed the required training specific for their responsibilities in this study. Furthermore, each member of the research team will be given a thorough explanation of the protocol and their responsibilities, including helping with scheduling, procedures, follow-up, data entry, or analysis. All research investigators will be required to complete proper training through their institutional review boards.

9.2 Use of Cancer Center Facilities

Patients will be evaluated and treated in at Sidney Kimmel Cancer Center at Johns Hopkins Hospital. All radiotherapy for this study will be performed in the department of Radiation Oncology at JHH. Other procedures related to this study (i.e., blood draws, fiducial placement, imaging studies) will be carried out at JHH.

9.3 Conflict of interest

There is no potential conflict of interest among the research personnel involved in this study.

10. **STUDY CALENDAR**

				Follow-Up ⁶ (Post-Radiation Treatment)					ent)
	Pre-Study	Pre-SBRT ⁹		4-6 weeks	4 mos	6 ⁴ mos	9 mos	12 ⁴ mos	Yrs 2-5 Q 3- 6 mos
Initial Consult	Х								
Demographics	Х								
History / Physical Exam	Х		SB	Х	Х	Х	Х	X	
Informed consent	Х		RJ						
Biopsy (confirmed adenocarcinoma)	Х		[Tre						
Labs: CBC, CMP, CA19-9		X^7	atr	Х	Х	Х	Х	X	Х
Research Blood Sample (optional)		X ⁷	nen	Х	Х	Х	X	Х	Х
Negative Pregnancy Test ⁸		Х	lt ^{10,}						
Seed Placement (EUS, CT, intraoperatively)		Х							
Research Biopsy (optional)		Х							
Simulation Scan		Х							
Radiologic Evaluation (CT ¹ , PET-CT ²)		Х		X ³	Х	Х	Х	Х	Х
Dynamic Whole Body PET/CT		X^{12}	X ¹²						
Research dMRI		Х							
QoL Questionnaire ⁵		Х		Х	Х	Х	Х	X	Х
AE Evaluation ¹³	Х			Х	Х	Х	Х	Х	Х
¹ CT pancreas or chest/abdomen/pelvis, as per	treating physician,	required pre- and po	st-SBRT. Hov	vever, may b	e supplemente	ed by PET/	CT (dual pha	se).	
² Pre-SBRT PET-CT scans and subsequent PE	T-CT scans are reco	ommended but not re	equired and m	ay be ordered	d at the discret	tion of the	treating phys	ician.	
³ If being reevaluated for resection, scans will	be conducted at 4-6	weeks or as determine	ned necessary	by treating	physician.				
⁴ It is preferred that patients have the 6MFU as submitted to SBRT treating facility. ⁵ QoL questionnaires may be completed and re	nd 12MFU evaluation eturned by mail or e	on and imaging at the mail if preferred.	e treating insti	tution. Othe	r evaluations	may be dor	ne at a local c	enter however	records must be
⁶ Follow-up appointments have a +/- 30 day to	lerance window. (e:	x. 6MFU may occur	between 5-7 1	nonths)					
⁷ Pre-SBRT labs should be done within 4 weel	ks prior to treatment	-							
⁸ Pregnancy test by urine or serum, for women	⁸ Pregnancy test by urine or serum, for women who are not post-menopausal as defined in Appendix III.								
⁹ Pre-SBRT procedures should be completed within 45 days of beginning treatment.									

¹⁰It is recommended that patients in both cohorts discontinue any chemotherapy one week prior to SBRT and delay resumption of chemotherapy until one week following completion of SBRT ¹¹Ideally all 5 fractions should be delivered Monday through Friday; however, treatment may be delivered over 2 weeks, as long as the patient receives at least 2 fractions per week.

¹² Required if participant consents to PET scan research correlative. To be performed at baseline and Day 5 SBRT ¹³Toxicity evaluation may be completed via telephone if participant cannot return for follow up.

11. MEASUREMENT OF EFFECT

11.1 Anti-tumor Effect

Patients will be evaluated for anti-tumor effect by follow-up imaging (pancreas protocol CT and/or PET-CT imaging) as outlined above. All subsequent scans (post-treatment) will be compared to the same pretreatment CT or PET/CT that was used in conjunction with radiation treatment planning.

11.1.1 Definitions

Patients will be evaluable for toxicity and evaluable for objective response at the follow-up intervals specified above.

11.1.2 Disease Parameters

Pancreatic and periampullary tumor response will be based upon standard radiographic criteria for the treated lesion and will be prospectively recorded in the JHU secure database. Radiographic response of the **pancreatic or periampullary tumor** by diagnostic CT scans will be defined **according to RECIST criteria as described below:**

CR = complete disappearance of index lesion

PR = at least 30% decrease in the longest diameter of the index lesion

PD = more than 20% increase in the longest diameter of the index lesion

SD = does not meet criteria for PR or PD

Pancreatic or periampullary tumor response will also be assessed by FDG-PET scans (when available) according to the following criteria:

CR = target lesion becomes photopenic or standardized uptake value (SUV) ratio of tumor/liver less than or equal to 1

PR = decrease in SUV ratio of tumor/liver (at least 30%) PD = increase in SUV ratio of tumor/liver (at least 20%)

SD = no significant change in SUV ratio of tumor/liver

Local tumor progression will be defined as $\geq 20\%$ increased size on CT scan compared to a CT scan from prior to treatment. Distant progression will be defined as any new tumor found outside of the pancreas or periampullary region on CT scan. Local and/or distant progression by both PET (if available) and CT scan will be recorded separately. We will also determine PET response with the new PERCIST criteria as reported by Wahl et al. (J Nuc Med 2009; 50:122S-150S).

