We recently presented the preliminary results of our phase II multi-center trial of gemcitabine (GEM) and fractionated Linac based SBRT to determine if a high rate of LPFS with reduced toxicity could be achieved. After multidisciplinary review, 32 pts with locally advanced PDA received GEM in sequence with Linac based SBRT (6.6 Gy in 5 consecutive daily fractions, 33 Gy total). LPFS, metastasis free survival (MFS), and overall survival (OS) were measured from date of tissue diagnosis. Objective tumor response (OTR) was assessed by RECIST/PERCIST. EORTC QLQ-C30/PAN26 questionnaires were used to measure QOL. Median f-up was 12 mos (range, 2-23). Mean age was 69.9 yrs (SD, 9.8) and 62% were male. Patients received a mean of 2.2 (SD, 1.0) GEM doses prior to SBRT and 8.3 (SD, 5.6) doses total. All pts completed SBRT. Median OS was 15.9 months (95% CI, 12.7-18.8). Stratification by CA19-9 > or < 90 at diagnosis yielded a hazard ratio of 6.2 for > 90(p=0.021). Median LPFS has not been reached and median MFS was 10.2 mos (95% CI, 2.9-17.5). LPFS rate at 1 year was 87%. OTR on CT was seen in 41%, while 41% had stable disease and 18% progressed. Tumor metabolic activity decreased in 17/18 patients with pre/post- Linac based SBRT PET available. Mean peak SUV was 4.0 pre- Linac based SBRT versus 2.4 post-Linac based SBRT (p=0.002). Median CA19-9 was reduced from 124.7 prior to SBRT to 43.9 afterwards. Acute toxicity included: grade 2 anorexia (37%), fatigue (28%), nausea (22%), abd pain (19%), weight loss (9%), diarrhea (3%); gr 3 nausea (9%); and gr 4 nausea (6%). Late gr \geq 3 GI toxicity was seen in 9%. Mean QOL score 4 wks post-Linac based SBRT was similar to baseline (p=0.38). At 6 most here was a trend towards improved QOL (p=0.07). Overall, fractionated Linac based SBRT with GEM achieved high rates of LPFS and tumor response. Minimal grade ≥ 3 acute and late toxicity was observed. Linac based SBRT is more likely to benefit patients with Ca-19-9 <90. A combination of Linac based SBRT with more aggressive chemotherapy may further improve outcomes.

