13. STATISTICAL CONSIDERATIONS

13.1 Endpoints

13.1.1 Primary Endpoint

To evaluate late (>3 months after Linac based SBRT) grade 2 or greater gastritis, fistula, enteritis, or ulcer, or any other grade 3 or greater gastrointestinal toxicity attributable to fractionated Linac based SBRT.

- 13.1.2 Secondary Endpoints
 - To determine rates of local progression free survival, overall survival, metastasis-free survival, and progression-free survival at 3, 6, and 12 months from Linac based SBRT.
 - To evaluate acute toxicity, defined as any grade 3 or greater gastrointestinal toxicity within 3 months of treatment.
 - To use FDG-(if available as per the recommendation by your treating physician) /CT scans for assessment of tumor response and progression.
 - To evaluate the role of FDG-PET scans in treatment planning.
 - To assess the quality of life before and after fractionated Linac based SBRT.
 - To further standardize Linac based SBRT delivery and dosimetric parameters.
 - To compare toxicity and outcomes among patients treated with fractionated Linac based SBRT delivered as 5 Gy x 5 (Cohort A of current protocol), 6.6 Gy X 5 (Cohort B of current protocol), 25 Gy X 1 (previous study), and 5-10 Gy x 3 (previous study).
 - To evaluate pain control (as define by pain medication requirements at 3, 6, and 12 months following Linac based SBRT.

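### The PET complete-response threshold in section 11.1.2 has no baseline condition and the categories have no order, so some low-uptake lesions qualify as both CR and SD, or both CR and PD

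*Combined protocol and SAP*

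**What the plan says.** Section 11.1.2 gives four PET categories based on the tumor/liver SUV ratio, to be used when PET is available.

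- CR has two limbs, loss of uptake or a fixed level: "CR = target lesion becomes photopenic or standardized uptake value (SUV) ratio of tumor/liver less than or equal to 1".
- PR is a fall of 30% or more: "PR = decrease in SUV ratio of tumor/liver (at least 30".
- PD is a rise of 20% or more: "PD = increase in SUV ratio of tumor/liver (at least 20".
- SD has no numerical limits and is not defined as the remainder: "SD = no significant change in SUV ratio of tumor/liver".

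Section 11.1 names the reference scan: "All subsequent scans (post-treatment) will be compared to the same pretreatment CT or PET/CT that was used in conjunction with radiation treatment planning". Section 8.2.1.1 makes that scan optional where PET is concerned: "Pre-Linac based SBRT PET scan is recommended but not required". Neither the eligibility criteria in section 4.1 nor section 11 sets a minimum baseline FDG uptake. PERCIST is to be determined as well, and nothing says which system governs.

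PET is put to use in section 13.1.2, which lists it among the secondary endpoints "for assessment of tumor response and progression", and in objective 1.2.3, which asks whether PET before and after treatment helps to predict local progression.

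**The concern.** The ratio limb of CR looks only at the follow-up value. The other categories look at change from baseline. Mixing the two is workable if the plan says which lesions may be called CR and which category wins when two apply. It says neither.

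The gap affects lesions at or below liver uptake before SBRT. They already satisfy the CR threshold, so a follow-up scan showing no change satisfies it again. Some that become more active satisfy it too, while also meeting PD.

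If such lesions are filed as CR, the best PET category contains lesions in which nothing improved and others in which uptake rose by a fifth or more. A PET response rate would then be too favourable, some PET progression would go uncounted, and any use of PET category as a predictor of local progression would be diluted. If different readers resolve the overlap differently, the readout is also not reproducible.

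**Working it through.** The plan gives no figure for this point, so there is nothing to reproduce. The check applies the written rules to pairs of ratios.

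**Inputs (section 11.1.2).** Let b be the pre-SBRT tumor/liver ratio and f the follow-up ratio.

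- CR (ratio limb): f ≤ 1
- PR: (f − b)/b ≤ −0.30
- PD: (f − b)/b ≥ +0.20
- SD: no significant change, without limits

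**CR and SD together.** If f = b and b ≤ 1, then f ≤ 1 and the change is 0%. Both definitions are met for every baseline up to 1.

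**CR and PD together.** PD needs f ≥ 1.2b and CR needs f ≤ 1. Both hold when 1.2b ≤ f ≤ 1, which requires b ≤ 1/1.2 = 0.833. For 0.833 < b ≤ 1, a 20% rise takes f above 1, so the lesion is PD only.

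**CR and PR together.** Both hold when f ≤ 1 and f ≤ 0.7b. The customary best-category order settles this one, although the plan does not state it.

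| b | f | Change | Categories met as written | Under the fix below |
|---|---|---|---|---|
| 0.90 | 0.90 | 0% | CR and SD | Not avid at baseline, no PD |
| 0.70 | 0.90 | 0.20/0.70 = +28.6% | CR and PD | PD |
| 0.80 | 0.96 | 0.16/0.80 = +20% | CR and PD | PD |
| 0.80 | 1.00 | 0.20/0.80 = +25% | CR and PD | PD |
| 0.85 | 1.00 | 0.15/0.85 = +17.6% | CR, not PD | Not avid at baseline, no PD |
| 0.90 | 1.08 | 0.18/0.90 = +20% | PD only | PD |
| 0.90 | 3.00 | 2.10/0.90 = +233% | PD only | PD |
| 1.50 | 0.90 | −0.60/1.50 = −40% | CR and PR | CR |
| 2.00 | 1.30 | −0.70/2.00 = −35% | PR only | PR |
| 1.50 | 1.60 | 0.10/1.50 = +6.7% | SD | SD |

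**Does other text remove the overlap?** Section 11.1 fixes the comparison scan, but the ratio limb of CR makes no use of a comparison. PERCIST is an additional system with no stated precedence. Neither resolves it.

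**The case against.** The best defence is grammatical. The verb in the CR definition implies change, and if it governs both limbs, CR would need a lesion that started above liver. The unchanged and CR/PD cases would then disappear. That may be what was intended. As written, though, the verb attaches to loss of uptake and the ratio limb stands as a bare threshold. A definition that depends on this reading should say so.

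The second defence is reach, and it stands. PET is optional before and after SBRT. Section 11.1.2 defines local progression by CT size and records PET and CT progression separately, so local progression-free survival cannot change. Sections 13.3 and 13.6 specify no analysis of PET categories and no model relating them to local progression, so the harm to objective 1.2.3 depends on the categories being used that way.

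Four stronger readings are tempting and are not supported.

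- *Non-avid lesions are complete responders before treatment.* Response is assigned only after treatment. Such lesions merely meet the threshold already.
- *Any rising low-uptake lesion is both CR and PD.* The conflict needs a baseline of 0.833 or less and a follow-up ratio no higher than 1.
- *CR is too easy because a fall from 1.1 to 1.0 (−9%) qualifies.* Calling uptake at or below liver a complete response is a defensible choice. It does mean that baselines between 1 and 1/0.7 = 1.43 can reach CR on a fall smaller than PR requires, but that is not the defect here.
- *The share affected can be estimated from section 3.3*, which reports "Mean peak SUV was 4.0 pre- Linac based SBRT versus 2.4 post-Linac based SBRT (p=0.002". Under an assumed log-normal spread (CV 30–50%) and an assumed liver SUV of 2.0–2.5, about 1–22% of lesions would start at or below liver. The liver value and the spread are not in the documents, and the mean is a peak SUV from a different, locally advanced cohort in which 18 of 32 patients had paired PET. The range reflects its assumptions and is not evidence about this trial.

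**Conclusion.** The gap is real and narrow. On a literal reading of section 11.1.2, CR and SD coincide for unchanged lesions with a baseline ratio of 1 or less. CR and PD coincide for baselines of 0.833 or less that rise at least 20% and stay at or below 1. This rests on reading the ratio limb as a bare threshold and on the absence of any avidity requirement or category order, both of which can be checked in the text.

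The consequence is possible misclassification in a secondary, optional PET readout and in whatever analysis serves objective 1.2.3. The toxicity endpoint, CT-defined local progression, sample size and stopping rules are untouched. How many patients would be affected is unknown and cannot be derived from the documents. A reader should not infer that the PET results would be broadly invalid; lesions starting above liver are classified without conflict apart from the CR/PR overlap, which the usual order settles.

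**What to change.** Keep the existing cut-offs and the photopenic limb in section 11.1.2, and add these rules:

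1. CR may be assigned only to a lesion with a pre-SBRT tumor/liver ratio above 1 that falls to 1 or below or becomes photopenic.
2. Lesions with a baseline ratio of 1 or less are not evaluable for PET CR or PR and are reported separately as not FDG-avid at baseline. They remain evaluable for PD, so that a clear rise such as 0.9 to 3.0 is still counted.
3. A rise of at least 20% from baseline is PD and outranks every other category.
4. CR outranks PR.
5. SD is everything else. In the non-avid group this means only that there was no PET progression, so it should be tabulated apart from SD in avid lesions.

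Once rule 1 is in place, CR and PD can no longer coincide, because a 20% rise from above 1 stays above 1; the ranking of PD is then a safeguard. A patient without a pre-SBRT PET has no baseline ratio and cannot be placed in these categories, which is worth stating.

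The change is to wording only and uses scans already taken. It should be made before the PET data are classified. The cost is that some patients with low baseline uptake leave the PET response denominator, and the PET CR rate may fall.
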